1.3. Dose Selection Rationale

[figure not shown]
A 60 mg qd dosing regimen in adults was found to be safe and effective in the pivotal Phase 3 trial in VTE patients. Based on in vitro data, it appears that edoxaban has similar activity in adults and neonatal cord blood. Hence, it is expected that doses that achieve similar exposures to the adult dose of 60 mg may be most effective in pediatric populations. This study is designed to safely evaluate exposures of a low- and high-dose in each pediatric cohort, in order to guide dosing in a Phase 3 study in pediatrics. The ex vivo study (TMCP-Peds-001) showed the anticoagulant effects of edoxaban are found to be similar between adult plasma and cord blood. Despite a difference in the baseline activity of various biomarkers, the potency of drug effects was similar between adults and cord blood. The current study is targeting to have similar plasma exposure as in the adult Phase 3 VTE study with low (30 mg) and high exposure (60 mg). For the younger age groups, it is planned to adjust the dose based on anticipated ontogeny differences and available data in the older pediatric age cohorts. The starting dose for adolescents low-dose group was selected on the basis of population PK modeling (PopPK) and simulations ([Figure 1.1](#)). The PopPK model was based on adult data (median age [range] 33 [18 to 85] years; median body weight [range] 75.8 [42 to 165 kg]). The basic structural model was a 2-compartment model with first-order absorption and lag time. The simulation dataset consisted of 12 typical male patients from 12 to 18 years. Body weight and height estimates were from the 2000 CDC (Centers for Disease Control and Prevention) Growth charts.⁷ Creatinine clearance values were calculated using the Schwartz equation.⁸ A total of 1,200 individuals were simulated. A simulated 30 mg dose appears to provide similar or slightly lower mean exposure in the adolescent population.

Figure 1.1: Simulated Plasma Concentration Time Profiles for Ages 12 to 18 Years (30 mg Dose)

Linear

Semi-logarithmic

1.4. Risks and Benefits for Study Patients

As described in United States regulations, this study is considered to fall into Title 21 Code of Federal Regulation (CFR) Part 50.53 as “Research involving greater than minimal risk and no prospect of direct benefit to individual subjects, but likely to yield generalizable knowledge about the subject's disorder or condition.”

The goal of this study is to identify pediatric doses that provide comparable exposure to adult efficacious doses in order to guide dose selection for Phase 3 studies in pediatrics.

In pediatric patients the proportion of children developing recurrent VTE ranged from 3% in neonates to 8% in older children and as high as 21% in children reported with a first idiopathic VTE. The results of meta-analyses indicate that 11% of children with nonidiopathic thrombosis overall develop a second VTE.¹¹ Hence, this study offers a platform by which the identification of patients with non-idiopathic thrombosis or those with potential recurrence may be identified for future therapeutic care.

In U157 study, the risk is considered as minimal for patients who already took anticoagulant therapy due to their health conditions. U157 is a single dose study with a sequential enrolment (from older to younger) and with two tested doses (“low” dose to achieve exposures comparable to a 30 mg adult dose and “high” dose to achieve exposures comparable to a 60 mg adult dose). U157 patients are NOT healthy children; their health conditions already exposed them to procedures necessary to address their health problems related to thromboembolism. In patients with no history of thromboembolic events, the risk is considered as a minor increase over minimal risk. U157 risk was estimated based on experience with similar treatments and procedures in the pediatric population¹² and from the well-known edoxaban effects in adults (Hokusai VTE Study). U157 is a dose finding study with safety as a secondary objective. The benefit to participate in U157 can be considered as direct for patients with health conditions exposing them to occurrence and/or recurrence of a thromboembolic event.

U157 study also presents a reasonable opportunity to further the understanding, prevention, or alleviation of a serious problem affecting the health or welfare of children with thromboembolic disease. The data derived from this study could potentially benefit pediatric patients when the study data is disclosed and becomes publically available or if it should lead to a possible update of the edoxaban label. In addition, doses derived from this study will be implemented in Phase 3 studies; in particular, patients with diagnosed VTE or cardiac diseases that may predispose them to venous or arterial thromboembolism.

The research will be conducted in accordance with sound ethical principles, and adequate provisions are made for soliciting the assent of the children and the permission of their parents or legal guardians.

The safety monitoring practices employed by this protocol (i.e., physical examinations, vital signs, AEs, and clinical laboratory assessments) in addition to periodic data review by a Data and Safety Monitoring Board (DSMB) are considered adequate to protect the patients’ safety.

Please refer to the Investigator’s Brochure¹ for the summary of clinical experience including side effects associated with edoxaban treatment.

1.5. Population, Route, Dosage, Dosage Regimen, and Treatment Period

The study population will include patients 38 weeks gestation to < 18 years of age of both sexes, who may require, or are currently on anticoagulant therapy.

These may include:

- Patients who have a recently acquired or Investigator determined ongoing risk of thromboembolic events (e.g., patients with thrombophilia, congenital heart disease, presence of a central venous catheter and prior venous thromboembolic event [VTE]).
- Patients who are completing their standard-of-care anticoagulant therapy. Note: that the dose of edoxaban should be at the time of the next scheduled standard-of-care anticoagulant administration:
 - At least 4 hours after last dose of unfractionated heparin.
 - At least 12 hours after last dose of bid low molecular weight heparin (LMWH).
 - At least 24 hours after last dose of qd LMWH and synthetic pentasaccharide (SP) Xa inhibitors.
 - For patients who were on a prior vitamin K antagonist (e.g., warfarin [C-U122] and any other anticoagulants) therapy, international normalization ratio (INR) value should be ≤ 2.5 prior to edoxaban dosing. If the patient's INR is > 2.5 , the patient's INR should be monitored until it is ≤ 2.5 .
- Patients who are currently treated for VTE with at least 5 days of heparin may interrupt their standard-of-care anticoagulant therapy for edoxaban administration. The dose of edoxaban should be:
 - At least 12 hours from last dose of bid LMWH, with a restart of LMWH 24 hours after edoxaban dose.
 - At least 24 hours from last dose of qd LMWH, with a restart of LMWH 24 hours after edoxaban dose.
- Patients with cardiac conditions who may require anticoagulant therapy.
- Patients with sickle cell disease who may require anticoagulant therapy.

For any condition, anticoagulant treatment interruption or discontinuation should not take place if the patient is at increased risk and should be appropriate as per standard care of practices.

The following dosage forms will be provided for this study:

- Edoxaban 30 mg oral tablets for patients 12 and < 18 years of age.
- Edoxaban granules for oral suspension (60 mg reconstituted with 8-mL water) to provide a 6 mg/mL suspension for oral administration for patients < 12 years of age.

In each age cohort, appropriated doses will be selected to achieve exposures comparable to adult doses of 30 mg (low-dose) or 60 mg (high-dose). If the observed exposure from the 30 mg dose in adolescents is higher than predicted and is comparable to the 60 mg adult dose exposures, then, the next cohort will receive a lower dose, instead of a higher dose. To allow for this

flexibility, patients in the 12 to < 18 years of age cohort will receive edoxaban tablets of 30 mg strength. Patients younger than 12 years of age will receive the edoxaban granule for oral suspension. The dose amount given to each patient will be determined based on emerging data. The dose given may be updated based on emerging data.

The PK model will be refined based on emerging data, modeling of a target age and weight range will establish dosing paradigms. The PK modeling will account for the range of weights.

1.6. Compliance Statement, Ethics, and Regulatory Compliance

This study will be conducted in compliance with this protocol, the ethical principles that have their origin in the Declaration of Helsinki, the International Conference on Harmonization (ICH) consolidated Guideline E6 for Good Clinical Practice (GCP) (CPMP/ICH/135/95), and applicable regulatory requirement(s):

- European Commission Directive (2001/20/EC Apr 2001)
- European Commission Directive (2005/28/EC Apr 2005)
- Food and Drug Administration GCP Regulations: CFR Title 21, parts 11, 50, 54, 56, and 312
- The Health Insurance Portability and Accountability Act as appropriate and/or
- Other applicable local regulations

1.6.1. Patient Confidentiality

The Investigator and the Sponsor will preserve the confidentiality of all patients taking part in the study, in accordance with GCP and local regulations.

The Investigator must ensure that the patient's anonymity is maintained. On the Case Report Form (CRF) or other documents submitted to Daiichi Sankyo, Inc. (DSI), patients should be identified by a unique patient identifier as designated by the Sponsor. Documents that are not for submission to DSI (e.g., signed Informed Consent Forms [ICF]) should be kept in strict confidence by the Investigator.

In compliance with federal regulations/ICH GCP Guidelines, it is required that the Investigator and institution permit authorized representatives of the company, of the regulatory agency(s), and the Independent Ethics Committee (IEC) or Institutional Review Board (IRB) direct access to review the patient's original medical records for verification of study-related procedures and data. The Investigator is obligated to inform the patient that his/her study-related records will be reviewed by the above-named representatives without violating the confidentiality of the patient.

1.6.2. Informed Consent Procedure

Before a patient's participation in the study, it is the Investigator's responsibility to obtain freely given consent and assent (generally, this age averages at 7 years of age), in writing, from the patient or legally acceptable representative after adequate explanation of the aims, methods, anticipated benefits, and potential hazards of the study and before any protocol-specific screening procedures or any study drugs are administered. A legally acceptable representative is an individual or other body authorized under applicable law to consent, on behalf of a

prospective patient, to the patient's participation in the clinical study. The written ICF should be prepared in the local language(s) of the potential patient population.

In obtaining and documenting informed consent, the Investigator should comply with the applicable regulatory requirements, and should adhere to GCP and to the ethical principles that have their origin in the Declaration of Helsinki. The consent form and any revision(s) should be approved by the IEC or IRB prior to being provided to potential patients.

The patient's written informed consent should be obtained prior to his/her participation in the study, and should be documented in the patient's medical records, as required by 21 CFR Part 312.62. The ICF should be signed and personally dated by the patient or a legally acceptable representative, and by the person who conducted the informed consent discussion (not necessarily the Investigator). The original signed ICF should be retained in accordance with institutional policy, and a copy of the signed consent form should be provided to the patient or legal representative. The date and time (if applicable) that informed consent was given should be recorded on the CRF.

If the patient or legally acceptable representative cannot read, then according to ICH GCP Guideline, Section 4.8.9, an impartial witness should be present during the entire informed consent discussion. This witness should sign the ICF after the patient or the legally acceptable representative has orally consented to the patient's participation and, if possible, signed the ICF. By signing the ICF, the witness attests that the information in the ICF and any other written information was adequately explained to and apparently understood by the patient or the legally acceptable representative and that informed consent was freely given by the patient or the legally acceptable representative.

Suggested model text for the ICF for the study and any applicable subparts (genomic, PK, etc.) and assent forms for pediatric patients (if applicable) are provided in the Sponsor ICF template for the Investigator to prepare the documents to be used at his or her site. Updates to applicable forms will be communicated via letter from the Clinical Study Manager.

According to 21 CFR 50.55 subpart b it states, "In determining whether children are capable of providing assent, the IRB must take into account the ages, maturity, and psychological state of the children involved. This judgment may be made for all children involved in clinical investigations under a particular protocol, or for each child, as the IRB deems appropriate." In 21 CFR 50.55 subpart g it states, "When the IRB determines that assent is required, it must also determine whether and how assent must be documented." For this study, the IRB will determine the age that is appropriate for the assent. Generally, this age averages at 7 years of age. The IRB will also determine the verbiage that may be added, as well as ensure the document is written at a level understandable to the population who will be signing the assent. The IRB may also require separate assent forms based on the age groups (i.e., separate assent forms for patients 7 to 12 years and for patients 13 to 17 years) to ensure the assents maintain their "maturity levels and understandability."

1.6.3. Regulatory Compliance

The study protocol, patient information and consent form, the Investigator's Brochure, or written instructions to be given to the patient, available safety information, patient recruitment procedures (e.g., advertisements), information about payments and compensation available to the

patients, and documentation evidencing the Investigator's qualifications should be submitted to the IEC or IRB for ethical review and approval according to local regulations, prior to the study start. The written approval should identify all documents reviewed by name and version.

Changes in the conduct of the study or planned analysis will be documented in a protocol amendment and/or the Statistical Analysis Plan.

The Investigator must submit and, where necessary, obtain approval from the IEC or IRB for all subsequent protocol amendments and changes to the informed consent document or changes of the investigational site, facilities or personnel. The Investigator should notify the IEC or IRB of deviations from the protocol or serious AEs (SAEs) occurring at the site and other AE reports received from DSI or Contract Research Organization (CRO), in accordance with local procedures.

As required by local regulations, the Sponsor's local Regulatory Affairs group will ensure all legal aspects are covered, and approval of the appropriate regulatory bodies obtained, prior to study initiation, and that implementation of changes to the initial protocol and other relevant study documents happen only after the appropriate notification of or approval by the relevant regulatory bodies.

2. STUDY OBJECTIVES AND HYPOTHESES

2.1. Study Objectives

2.1.1. Primary Objectives

The primary objective of this study is to characterize the PK of edoxaban in pediatric patients following single-dose oral administration.

2.1.2. Secondary Objectives

The secondary objectives of this study are:

- To evaluate the PD effects of edoxaban in pediatric patients following single-dose oral administration
- To evaluate the safety and tolerability of single-dose oral administration of edoxaban in pediatric patients
- To assess metabolite exposure (D21-2393, D21-3231, D21-1402, and D21-2135) in pediatric patients
- To evaluate the palatability (bitterness, sweetness, and overall taste or aroma) of the liquid oral suspension of edoxaban

2.1.3. Exploratory Objectives

No exploratory objectives are planned for this study.

2.2. Study Hypothesis

This is the first edoxaban pediatric study and is not intended to test a hypothesis, but rather to generate information that will allow dose selection for subsequent clinical efficacy/safety studies in pediatrics.

3. STUDY DESIGN

3.1. Overall Plan

3.1.1. Study Type

This is a Phase 1, open-label, single-dose, non-randomized, multiple-center PK and PD study in pediatric patients. The study will include 5 pediatric age cohorts with evaluation of 2 different doses within each age cohort (low- and high-dose).

Age cohorts and dose groups:

- 12 to < 18 years of age on the day of dosing (12 evaluable total patients)
 - Cohort 1a: Low-dose group (6 patients)
 - Cohort 1b: High-dose group (6 patients)
- 6 to < 12 years of age on the day of dosing (12 evaluable total patients)
 - Cohort 2a: Low-dose group (6 patients)
 - Cohort 2b: High-dose group (6 patients)
- 2 to < 6 years of age on the day of dosing (12 evaluable total patients)
 - Cohort 3a: Low-dose group (6 patients)
 - Cohort 3b: High-dose group (6 patients)
- 6 months to < 2 years of age on the day of dosing (12 evaluable total patients)
 - Cohort 4a: Low-dose group (6 patients)
 - Cohort 4b: High-dose group (6 patients)
- 38 weeks gestation to < 6 months of age on the day of dosing (12 evaluable total patients)
 - Cohort 5a: Low-dose group (6 patients)
 - Cohort 5b: High-dose group (6 patients)

A total of 60 patients will be enrolled such that 12 evaluable patients will be in each age cohort and 6 patients will be within each dose group. Dropouts or patients with unusable data (for reasons other than AEs) may be replaced.

3.1.2. Treatment Groups

Patients will be dosed orally with a single dose of edoxaban on Day 1. Patients in the 12 to < 18 years of age cohort will be dosed with multiples of edoxaban tablets of 30 mg strength. Patients younger than 12 years of age will receive the edoxaban granule for oral suspension. The dosing amount and formulation type may change based on emerging data.

If a patient is unable or unwilling to ingest the assigned dosing form (tablet or suspension formulation), the patient will not be enrolled and will be replaced.

Patients will be administered edoxaban in the morning with water.

- Cohorts 1a/1b: 120 mL water;
- Cohorts 2a/2b: 60 mL water;
- Cohorts 3a/3b: 40 mL water;
- Cohorts 4a/4b: 10 mL water;
- Cohorts 5a/5b: 10 mL water.

Patients will be asked to fast for at least 4 hours before dosing and for an additional 2 hours after dosing. If this is not feasible because of the patient's age or other needs, (unflavored) milk, or an equivalent substitute liquid (but not fruit juices), will be allowed until 1 hour before and starting at 1 hour postdose. During this period, the total volume of liquids should not exceed 240 mL, excluding the volume of water utilized for dosing.

Order of enrollment will be from the oldest age cohort to the youngest age cohort. Within each age cohort, enrollment will first start in the lower dose group (to achieve exposures comparable to a 30 mg adult dose). After evaluation of PK and safety data from at least half the patients in the lower dose group, enrollment may then start in the higher dose group (to achieve exposures comparable to a 60 mg adult dose). If the observed exposures are higher than expected in the lower dose group and exceed the projected 60 mg adult exposure, then a lower dose may be investigated in the proposed "high-dose" group. Enrollment in the next younger age cohorts will begin when at least 50% of patients have completed the study in the older age cohort.

Enrollment in the younger age cohorts will start only after PK and safety data have been evaluated from at least 6 patients (3 low-dose and 3 high-dose) in the older age cohort.

Pharmacokinetic and safety data will be reviewed by a DSMB (see Section 11.9) who will approve the start of the next younger age cohort. However, enrollment initiation of Cohort 5 may be considered without PK and safety data from at least 50% of patients in the preceding older dose group.

In Cohort 1, the oldest age group (12 to < 18 years), doses have been selected on the basis of modeling of adult data to target comparable exposures to 30 mg (low-dose) and 60 mg (high-dose). In this cohort, fixed dosing will be used. In Cohorts 2, 3, 4, and 5, the younger age groups (38 weeks gestation to < 12 years), appropriated doses will be selected to elicit target exposures comparable to those achieved from adult doses of 30 mg (low-dose) or 60 mg (high-dose). Patients in Cohort 1 will receive multiples of edoxaban tablets of 30 mg strength. Patients in Cohorts 2, 3, 4, and 5 will receive the edoxaban granule for oral suspension. The dose that each dose group receives will be determined by Daiichi Sankyo based on emerging PK data and modeled doses needed to achieve target exposures.

Study duration will be approximately 4 weeks for each patient, which will include a screening period (within 21 days of dosing), a treatment period, and a follow-up visit conducted within 10 days after dosing. However, a patient will be considered to have completed the study if they provide the last scheduled PK sample. The treatment period will consist of predose procedures occurring on Day -1 or 1, dosing on Day 1, and postdose procedures occurring postdose on Days 1, 2 (all cohorts) and Day 3 (all patients enrolled prior to Version 5.0 of the protocol may have had Day 3 PK samples obtained). The treatment period days may occur as in-patient or

out-patient based on the clinic's ability/discretion. The overnight stays are not mandatory. Check-out procedures will be performed after the last PK/PD blood samples are collected (Day 2 or Day 3).

An attempt will be made to have a balanced distribution of ages in each age cohort and dose group to provide maximum information regarding PK/PD and safety/tolerability.

In each age cohort, appropriated doses will be selected to target exposures comparable to adult doses of 30 mg (low-dose) or 60 mg (high-dose). This will be done on an ongoing basis, whereby emerging PK concentration-time data from completed patients will be analyzed on an ongoing basis and used to predict the doses required to obtain targeted exposures in upcoming age cohorts and dose groups. Additionally, this ongoing PK analysis will be used to refine and optimize the PK blood sampling scheme (number of samples and timing) in upcoming age cohorts and dose groups.

Refer to the Schedule of Events (Appendix [17.7](#)) and study procedures (Section [6](#)).

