4. STUDY POPULATION

4.1. Enrollment

The Investigator will maintain a confidential screening log of all potential study candidates that includes limited information of the patients (initials, age [derived], and sex), date, and outcome of the screening process (e.g., enroll in the study, reason for ineligibility, and refused to participate).

The Investigator will be expected to maintain an enrollment log of all patients enrolled in the study indicating their assigned study number.

The Investigator will maintain a confidential patient identification code list. This confidential list of names of all patients allocated to study numbers on enrolling in the study allows the Investigator to reveal the identity of any patient, when necessary.

Patients will be considered enrolled upon obtaining informed consent (assent, when applicable) at randomization.

Each patient or legally acceptable representative will sign an ICF and assent, if applicable, as required by country-specific regulatory authorities. For additional information on informed consent, see Section [1.6.2](#).

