6.3.3. Treatment Period (Days 1 to 3)

6.3.3.1. Day 1

On Day 1, the following procedures will be performed after the patient has fasted for at least 4 hours (patients will continue to fast until 2 hours postdose). Patients who have not fasted must return on a subsequent day for Day 1 treatment. Any procedure occurring after hour 8 on Day 1 may be performed using a home healthcare service, depending on the availability of the service in the patient's country:

- **All Cohorts:**
 - Edoxaban administration.
 - Assessment of palatability for patients or guardians of patients receiving the edoxaban granule for oral suspension formulation (including bitterness, sweetness, overall taste, and aroma) using 100 mm VAS.
 - AE monitoring.
 - Concomitant medication monitoring.
- **Cohort 1:**
 - Vital signs (including, blood pressure, pulse rate, and body temperature) will be taken before dose administration and within the following windows: 0.25 to 1 hour, 1.5 to 3 hours, and 8.5 to 14 hours postdose. All vital sign assessments will be performed before the scheduled blood sampling for edoxaban and after at least a 5-minute rest in a sitting or supine position. The position in which the vital signs are taken (i.e., sitting or supine) will be recorded in the CRF.

- Serial PK blood samples will be collected after edoxaban administration using a window approach at 0.25 to 1 hour, 1.5 to 3 hours, 3.5 to 6 hours, 6.5 to 8 hours, and 8.5 to 14 hours postdose.
- Serial PD blood samples for estimation of biomarkers of coagulation (aPTT, PT, and anti-FXa) will be collected at predose and immediately after simultaneously scheduled PK sample collections at 0.25 to 1 hour, 1.5 to 3 hours, 3.5 to 6 hours, and 6.5 to 8 hours.
- **Cohorts 2 and 3:**
 - Vital signs (including, blood pressure, pulse rate, and body temperature) will be taken before dose administration and within the following windows: 0.25 to 1 hour, 1.5 to 3 hours, and 9 to 14 hours postdose. All vital sign assessments will be performed before the scheduled blood sampling for edoxaban and after at least a 5-minute rest in a sitting or supine position. The position in which the vital signs are taken (i.e., sitting or supine) will be recorded in the CRF.
 - Serial PK blood samples will be collected after edoxaban administration using a window approach at 0.25 to 1 hour, 1.5 to 3 hours, 4 to 8 hours, and 9 to 14 hours postdose.

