10. OTHER ASSESSMENTS

Formulation Palatability

Patients receiving the edoxaban granule for oral suspension formulation who are developmentally capable of providing an accurate response will be asked to rate several aspects of palatability (including bitterness, sweetness, overall taste, and aroma) using 100 mm VAS. The VAS questionnaire will be provided to the sites by Medpace.

Patients who are old enough will score the VAS themselves. For younger children, the parents will provide this information, if possible. For the youngest children, there will be free text input available, to provide information on whether the patient spit it out and may not have liked the flavor, etc.

VAS and text responses will be measured and/or recorded on the CRF. Refer to Appendix [17.6](#) for the VAS.

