11.1.3. Safety Analysis Set

The safety analysis set will include all patients who received edoxaban.

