11.7. Other Analyses

11.7.1. Palatability Analyses

The VAS scores for palatability will be listed and summarized by age cohort and/or dose group using descriptive statistics, if data permit.

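### Children who refuse the suspension at dosing are replaced and counted in no planned palatability output, so the secondary palatability result can look too favourable

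*Combined protocol and SAP*

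**What the plan says.** Section 2.1.2 lists among the secondary objectives: "To evaluate the palatability (bitterness, sweetness, and overall taste or aroma) of the liquid oral suspension of edoxaban". Under Section 3.1.2, Cohort 1 takes tablets and everyone under 12 years takes the suspension.

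On children who do not take the assigned form, Section 3.1.2 says: "If a patient is unable or unwilling to ingest the assigned dosing form (tablet or suspension formulation), the patient will not be enrolled". The same sentence ends by saying that such a child is replaced. The synopsis repeats the rule, and it covers tablets as well as the suspension.

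Section 4.1 fixes enrolment by a different event: "Patients will be considered enrolled upon obtaining informed consent (assent, when applicable) at randomization".

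Section 6.3.3.1 schedules on Day 1: "Assessment of palatability for patients or guardians of patients receiving the edoxaban granule for oral suspension formulation". Table 17.1 places the VAS in the dosing column and nowhere else.

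Section 11.7.1 gives the whole palatability analysis: "The VAS scores for palatability will be listed and summarized by age cohort and/or dose group using descriptive statistics, if data permit". Section 11.1 defines PK, PD and safety sets but no palatability set.

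Some rejection data are collected. Section 5.1.2 has staff record any suspension spat out or drooled. Section 10 provides free text for the youngest children, "to provide information on whether the patient spit it out and may not have liked the flavor, etc", and has text responses recorded on the CRF.

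**The concern.** A child who refuses the suspension because of its taste has one of the least favourable palatability outcomes there is. Under Section 3.1.2 that child is treated as never enrolled, and another child fills the place. The replacement contributes a VAS score if he or she takes the dose, and the refuser contributes none. The summary then describes palatability conditional on the dose being taken, and nothing beside it says how many children were offered the suspension.

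At stake is the reading of a secondary objective. The study is meant to guide paediatric Phase 3 work, and a reader of the palatability table could not tell a well-accepted formulation from one whose refusers had been replaced. The mismatch with Section 4.1 also leaves the disposition status of such a child undefined.

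**Working it through.** The documents give no figure for palatability. The power statement in Section 11.10 concerns CL/F and V/F only and is unaffected. The check is mainly a comparison of sections.

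**1. When can a refusal show itself?** Sections 4.1.1 and 4.1.2 contain no criterion on willingness or ability to take the dosing form. Neither screening (6.1) nor check-in (6.3.2) includes a taste or swallowing trial. The first scheduled contact with the suspension is Day 1 dosing (6.3.3.1). A refusal in response to taste can therefore appear only then.

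**2. What is the child's status at that moment?** Section 4.1 ties enrolment to consent at randomization. Section 6.2 says the study is not randomized, so the exact moment is unclear. Consent is obtained at screening, and a dose group must be assigned before a dose can be offered, so on either reading the child is enrolled before Day 1 dosing. Section 3.1.2 says the same child is not enrolled, yet also says the child is replaced, which implies that a place had been taken.

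**3. Where would the refusal be reported?**

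| Source | Captures an outright refusal? | Planned palatability output? |
|---|---|---|
| VAS (6.3.3.1, 10) | No: rated for those receiving the suspension | Yes (11.7.1) |
| Spit-out and drooling check (5.1.2) | Not explicitly: suspension spat out or drooled | None |
| Free text (10) | Possibly, youngest children only | None |
| Screening log (4.1) | Screening outcomes; no stated category for refusal at dosing | None |
| Disposition (11.3) | No refusal category named | None |

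**4. How large is the effect?** Let p be the proportion of children offered the suspension who refuse, T the mean VAS score among those rated, and R the mean the refusers would have given. Then

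- mean over all offered = (1 − p) × T + p × R
- reported mean minus that mean = p × (T − R)

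Only T is observed. Neither p nor R is given or collected, so no shift in millimetres can be calculated. The VAS anchors are also not visible in the text.

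**5. Illustrative counts only.** If refusers are replaced until N children take the dose, the expected number replaced is N × p / (1 − p). The refusal rates below are assumptions, and zero is possible.

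| Assumed p | Per cohort (N = 12) | Four suspension cohorts (N = 4 × 12 = 48) |
|---|---|---|
| 0% | 0 | 0 |
| 5% | 12 × 0.05 / 0.95 = 0.6 | 2.5 |
| 10% | 12 × 0.10 / 0.90 = 1.3 | 5.3 |
| 20% | 12 × 0.20 / 0.80 = 3.0 | 12.0 |
| 30% | 12 × 0.30 / 0.70 = 5.1 | 20.6 |

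Whatever the true rate, the planned palatability summary would show none of these children.

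**The case against.** The strongest reply is that Section 3.1.2 is an eligibility rule. It covers tablets too, says nothing about taste, and could be applied before any child meets the suspension. A child judged unwilling beforehand tells us nothing about palatability. This stands as far as it goes: the timing is unclear, and not every refusal reflects taste. But the plan has no step at which such a judgement is made before Day 1, and even a pre-dose filter would leave the summary conditional on willingness.

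A reader might infer that refusals disappear from the record. The documents do not support that. Spit-out and drooling are recorded for suspension patients, free text is kept for the youngest, and Section 4.2 asks for reasons for withdrawal. What is missing is a planned palatability output that uses any of this.

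A reader might also infer that only children who liked the suspension are scored. That too goes beyond the text. A child can take the dose and rate it badly, a parent can answer for a younger child, and Section 11.7.1 does not require that the dose was swallowed.

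Nor is there a gap in the safety analysis for a child who takes a little and then refuses. Section 11.1.3 is clear: "The safety analysis set will include all patients who received edoxaban". Enrolment status does not enter.

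Finally, the analysis is descriptive, no acceptability claim or threshold is planned, and Section 11.2 defers full detail to a separate SAP. All of this is fair, and it limits the weight of the point. No refusal count appears in the text at hand, and a descriptive result still needs its denominator.

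**Conclusion.** The point holds in a limited form. Followed as written, the plan makes the palatability result conditional on the child receiving the suspension, counts no outright refusals, and has no denominator of children offered it. The direction is toward a more favourable result if refusers would have rated the suspension worse than takers, which is plausible where taste is the reason.

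The size is unknown. It could be nil if no child refuses, and the documents give no rate from which to estimate it. A stated bias in millimetres, or a score imputed for refusers, would be invention: the scale directions are not visible, and a worst score is not defined for a scale such as sweetness.

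The conclusion assumes that refusals occur at Day 1 dosing and that no separate analysis document already tabulates them. The disagreement between Sections 3.1.2 and 4.1 on who is enrolled does not depend on either assumption. This is a cheap improvement to a secondary, descriptive objective and does not touch the PK analysis.

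**What to change.** In Section 3.1.2, the synopsis and Section 11.7.1:

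- Define the palatability set as all children in Cohorts 2 to 5 who are offered the suspension on Day 1.
- Record one outcome for each: taken in full, partly taken or spat out, or refused, with the reason. The spit-out check in Section 5.1.2 already supplies part of this.
- Report each outcome as a number and percentage of children offered, by age cohort and dose group, beside the VAS summary. State whether the child or a parent gave the rating.
- Do not impute VAS scores for refusers.

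Reconcile the not-enrolled wording in Section 3.1.2 and the synopsis with the enrolment definition in Section 4.1, and clarify what randomization means there, since Section 6.2 says there is none. Replacement for PK purposes may stay.

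The cost is one CRF field and one table, with no extra patients, visits or blood.
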